In this study, we will enroll female pediatric emergency department (ED) patients presenting with a diagnosis of abdominal pain who may have a transabdominal pelvic ultrasound ordered by their treating physician (or nurse practitioner). In order to maximize the visualization of organs deep within the pelvis such as the ovaries and uterus, the patient's bladder must be full. The current practice at our institution, as well as numerous others, is to have a bladder catheter placed immediately when a transabdominal pelvic ultrasound is ordered, and then to fill the bladder in a retrograde manner in order to provide enhanced visualization of the pelvic structures. The process of inserting a bladder catheter into a pediatric patient is an invasive procedure which can be traumatic and painful to the patient. Additionally, if the patient's bladder is already full, this procedure may be unnecessary.

In this study, a point-of-care bladder ultrasound will be performed, upon enrollment of a patient by a study bedside sonographer (our pediatric emergency department nurse practitioners), to assess degree of bladder fullness. This measurement will then be repeated serially while the patient is receiving hydration and the ultrasound will be performed when the bladder is full. We hypothesize that this work flow will result in an equivalent time to transabdominal pelvic ultrasound completion and will reduce the number of potentially traumatic and painful, invasive urethral bladder catheterizations.

b. Describe how outcomes will be measured for this protocol. The primary outcome variable will be time to completed pelvic ultrasound, described as time from transabdominal pelvic ultrasound order placed to time of transabdominal pelvic ultrasound image completion.

Secondary outcomes include: proportion of urethral bladder catheterizations and patient's pain level with the process of point-of-care bladder ultrasound vs. bladder catheterization, as measured using Visual Numerical Rating Scale (VNRS) (see attached).

15. Background - in nontechnical, lay language

Summarize in 2-3 paragraphs past experimental and/or clinical findings leading to the design of this protocol. Include any relevant past or current research by the PI. For drug and device studies, summarize the previous results (i.e., Phase I/II or III studies).

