Describe your ability to obtain access to the proposed population that will allow recruitment of the necessary number of participants: **This will be a convenience sample, identified based on treating physician's suspicion that a transabdominal Pelvic Ultrasound/Ovarian Torsion Ultrasound (Order-set) will be placed and for whom arrival to the ED is between the hours of 0700-2300 on Mondays-Fridays, as this correlates with the times that sonographers are in-house, and hence real-time attainment, of transabdominal pelvic ultrasounds is achievable.**

d. Describe the inclusion/exclusion criteria:

Inclusion Criteria:

- Age 8yr-18yrs
- Female
- Likely to have order placed for transabdominal pelvic ultrasound/ovarian ultrasound

- No history of pelvic or bladder reconstructive surgery

Exclusion Criteria:

- Pregnancy (known)
- Critically ill patients
- Patients with known renal or genitourinary structural abnormalities or prior pelvic/GU surgery
- Chronic renal disease
- Patients presenting outside the defined treatment windows

- e. If participants will comprise more than one group or stratification, describe each group (e.g., treatment/intervention, placebo, controls, sham treatment) and provide the number of participants anticipated in each group.

Treatment (2-Scan) Group: N = 24

The group randomized to undergo point-of-care ultrasound to assess bladder fullness, initially and at 30min increments until achieving qualitatively “full” measures by point-of-care ultrasound. When the bladder is determined to be full, the transabdominal pelvic ultrasound will be performed.

Control Group= N= 24

The group randomized to undergo standard practice, which is to place indwelling urethral bladder catheter for purpose of retrograde bladder filling prior to transabdominal pelvic ultrasound.

- f. Indicate which, if any, of the special populations listed below will be involved in the protocol. Include the Special Populations Review Form (SPRF) if indicated.

- Pregnant Women: Attach SPRF—Pregnant Women, Fetuses, Neonates/Nonviable Neonates
- Fetuses: Attach SPRF—Pregnant Women, Fetuses, Neonates/Nonviable Neonates
- Neonates/Nonviable Neonates: SPRF—Pregnant Women, Fetuses, Neonates/Nonviable Neonates
- Prisoners: Attach SPRF—Prisoners
- Minors (<18 years old): Attach SPRF—Minors
- Employees or students at institution where research conducted
- Persons who are temporarily decisionally impaired
- Persons who are permanently decisionally impaired
- Non-English Speakers

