- a. Describe the procedures for all aspects of your protocol. Tell us what you are doing.

This study enrolls patients presenting to the pediatric ED for clinical complaints including, but not limited to, abdominal or pelvic pain, and for whom the treating physician/nurse practitioner anticipates ordering a transabdominal pelvic/ovarian torsion ultrasound.

Once it has been determined that the participant is eligible, and has provided written informed consent (or legal guardian), or assent (when appropriate), the patient will be randomized into the control or the treatment group. The control group will undergo the standard care where bladder catheterization and timing of imaging is at the treatment team's discretion.

In the intervention group, a study member who has completed asynchronous didactic and hands-on training in bladder ultrasound (see attached summary of US education) will perform a point-of-care bladder ultrasound for qualitative assessment of bladder fullness, using a SonoSite Exporte or SonoSite M-Turbo ultrasound machine. The exam will be performed during a time that does not interfere with the patient's care. This ultrasound will be obtained immediately upon enrollment and serially at 30-minute intervals until the bladder is determined to be full, either by a qualitative ultrasound bladder measurement (attached) OR by patient's sensation of bladder fullness (Bladder Fullness Scale, attached). Bladder Fullness Scale is a 4-point scale which is adopted from a urology bladder sensation measurement tool and has been used in previous, similar research.

If the bladder is not full by this qualitative assessment, the patient will receive additional hydration during the interval between repeated ultrasound examinations. This hydration will be provided by either an oral or intravenous route. The decision on administration of intravenous fluids will be made by the treating physician. Repeated point-of-care ultrasounds to assess bladder fullness will be attained at 30-min increments, or when a patient has the sensation of maximal fullness.

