Time to successful transabdominal pelvic ultrasound will be recorded. Bladder ultrasound images will be stored securely and reviewed by blinded ultrasound fellowship-trained or RDMS-certified attending emergency/pediatric emergency physicians to determine inter-rater reliability of the bedside ultrasound interpretation as well as for quality assurance. Such review will be conducted on a weekly or bi-weekly basis. A kappa of 0.6 to be considered excellent correlation.

At the conclusion of the intervention, the patient (or guardian, based on age), will be provided a survey regarding their satisfaction of the interventions, length of stay, and comfort level.

The following information will be recorded from the participant’s medical record:

- Volume of PO or IVF consumed
- Time of order of transabdominal pelvic ultrasound
- Time of completion of transabdominal pelvic ultrasound (as determined by time stamped on radiology report)
- Total ED length of stay, in minutes
- Door to MD/NP time, in minutes
- Outcome/condition at discharge
- MRN
- Visit Date
- Any adverse outcomes—complications with foley, severe pain, etc.
- Discharge diagnosis
- Patient weight (in kg)
- Patient age (in months/years)
- Race

b. What is the probable length of time required for the entire protocol (i.e., recruitment through data analysis to study closure)? **2 years**

c. What is the total amount of time each participant will be involved? Each participant’s time involved will vary, but is limited to the hospital length of stay. Interaction with each participant will last the amount of time needed to perform the consent process and the exam.

d. If different phases are involved, what is the duration of each phase in which the participants will be involved? If no phases are involved, enter “None.” **None**

e. List the procedures, the length of time the procedure takes, the total # of times the procedure is performed, and indicate whether each is performed solely for research or would already be performed for treatment or diagnostic purposes (routine care) for the population.

-Insert additional table rows as needed.

-If procedure is sometimes research and sometimes routine care, include on separate lines with number of times as each.

Procedure	Length of Time Required of Participants	Total # of Times the Procedure is Performed	Research (Res) –OR- Routine Care

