ii. Describe any other alternative treatments or interventions: Alternatives: 1) relying on patient's subjective perception of bladder fullness, or 2) attempts at transabdominal pelvic ultrasound after empiric "bladder filling" without point-of-care ultrasound visualization, such as arbitrary PO fluid consumption or IV fluid administration

iii. Describe any withholding of, delay in, or washout period for standard of care or alternative treatment that participants may be currently using: If participants in the treatment group comply with treatment protocol, urethral bladder catheterization could be avoided altogether or could be delayed, per treating physician's/nurse practitioner's discretion, and performed later if time to successful "full" bladder by point-of-care assessments and active hydration, were unsuccessful. Additionally, any participant who consents/assents, and then wishes to withdraw will immediately be converted to standard of care, which could mean routine performance of invasive urethral bladder catheterization, or other measures, at treating physician's/nurse practitioner's discretion.

d. Do you foresee that participants might need additional medical or psychological resources as a result of the research procedures/interventions? Yes No

If Yes, describe the provisions that have been made to make these resources available. N/A

e. Do the benefits or knowledge to be gained outweigh the risks to participants?

Yes No

If No, provide justification for performing the research: N/A

20. Precautions/Minimization of Risks

a. Describe precautions that will be taken to avoid risks and the means for monitoring to detect risks. This study is minimal risk. The PI and study staff will monitor for cues that participants are experiencing physical discomfort or are otherwise too ill to participate.

If the protocol involves drugs or devices skip Items 20.b. and 20.c. and go to Item 21. Instead include this information in the Drug Review Sheet or Device Review Sheet, as applicable.

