- b. If hazards occur to an individual participant, describe (i) the criteria that will be used to decide whether that participant should be removed from the protocol; (ii) the procedure for removing such participants when necessary to protect their rights and welfare; and (iii) any special procedures, precautions, or follow-up that will be used to ensure the safety of other currently enrolled participants. **Because this study is minimal risk, we have not established criteria that would be used to remove a participant from the protocol, or established procedures for removing participants or following other participants for safety. Any decision to remove a participant from the study would be made by the study PI, the patient/family, or the treating physician.**
- c. If hazards occur that might make the risks of participation outweigh the benefits for all participants, describe (i) the criteria that will be used to stop or end the entire protocol and (ii) any special procedures, precautions, or follow-up that will be used to ensure the safety of currently enrolled participants. **Because this study is minimal risk, we have not established criteria that would be used to remove a participant from the protocol, or established procedures for removing participants or following other participants for safety. Any decision to remove a participant from the study would be made by the study PI, the patient/family, or the treating physician.**

21. Informed Consent

- a. Do you plan to obtain informed consent for this protocol? Yes No
If Yes, complete the items below.
If No, complete and include the Waiver of Informed Consent or Waiver of Authorization and Informed Consent, as applicable.
- b. Do you plan to document informed consent (obtain signatures) for this protocol? Yes No
If Yes, complete the items below.
If No, complete the items below and include the Waiver of Informed Consent Documentation.
- c. How will consent be obtained? **Study staff will be notified by the treating physician (or nurse practitioner) or bedside nurse that the patient is presenting with a complaint for which a transabdominal pelvic ultrasound may be ordered. If the patient appears to be eligible, and who matches the inclusion criteria, then a member of the study staff will approach the patient, explain the study and request written informed consent.**
- d. Who will conduct the consent interview? **A member of the study staff.**

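### The primary outcome is timed from the ultrasound order, but patients are randomised before an order need exist, so time zero can be set after allocation

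*Protocol*

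**What the plan says.** All references are to the protocol; no SAP was available.

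- **Clock.** Section 14.b defines the primary outcome as a duration, "described as time from transabdominal pelvic ultrasound order placed to time of transabdominal pelvic ultrasound image completion". Section 14.a hypothesises that this time will be equivalent in the two workflows.
- **Entry.** The inclusion criterion in Section 16.d is "Likely to have order placed for transabdominal pelvic ultrasound/ovarian ultrasound". Section 17.a describes patients whose clinician "anticipates ordering a transabdominal pelvic/ovarian torsion ultrasound". Under Section 21.c, staff seek consent after being told that "the patient is presenting with a complaint for which a transabdominal pelvic ultrasound may be ordered".
- **Randomisation.** Section 17.a says that after eligibility and consent "the patient will be randomized into the control or the treatment group". It does not require an order to be in place.
- **Start of each workflow.** Treatment-arm scanning begins at enrolment and repeats every 30 minutes (17.a). In current practice the catheter follows directly on the order (14.a), and in the control arm the team decides when imaging happens (17.a).
- **Who knows the arm.** For treatment-arm patients whose bladder is not yet full, "The decision on administration of intravenous fluids will be made by the treating physician" (17.a). Under Section 19.c.iii, "urethral bladder catheterization could be avoided altogether or could be delayed" in that arm at the treating clinician's discretion. Only the reviewers of stored bladder images are described as blinded (17.a).
- **Times recorded.** The medical-record list in Section 17.a includes "Time of order of transabdominal pelvic ultrasound" and the completion time, but no randomisation time. Section 23.a mentions an enrolment log without saying that it holds a time. The time may be recorded elsewhere.

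**The concern.** Randomisation makes the arms comparable from the moment of allocation. An outcome whose start point comes later, and can be influenced by knowledge of the arm, is protected only if that start point is timed alike in both arms. Nothing in the protocol ensures this.

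Two opposite behaviours are both compatible with the text. A clinician with a treatment-arm patient might hold the order until the bladder is full. Scanning and hydration then fall before time zero and are not counted. Or the clinician might order at once, so that the whole filling period counts, while control-arm orders are placed only when the team is ready to proceed. The first hides a real delay; the second creates a false one. Because the trial hopes to show equivalent time, a hidden delay would support its hypothesis wrongly.

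**Working it through.** **Inputs from the protocol.** 24 patients per arm (16.e), 48 in total (16.a); 24 + 24 = 48. The protocol gives no SD, margin, alpha or power, so there is no stated precision to reproduce. The SDs and lags below are assumptions, used for scale only.

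**Step 1: the identity (no assumptions needed).** Let R be randomisation, O the order and C image completion. For each patient

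(C − O) = (C − R) − (O − R).

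Taking means and subtracting control (C arm) from treatment (T arm):

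difference on the order clock = difference on the randomisation clock − (lag_T − lag_C),

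where lag is the mean of O − R. The bias relative to the randomised comparison is −(lag_T − lag_C), which is zero when the lags are equal. Example: if the treatment arm truly takes 30 min longer from randomisation and its orders come 30 min later (one scan interval), the primary outcome shows 30 − 30 = 0.

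**Step 2: scale against sampling error.** SE = SD × √(2/24). Coverage of a 95% CI under bias is Φ(1.96 − d) − Φ(−1.96 − d), with d = |bias|/SE. Coverage is 90% at d = 0.652 and 80% at d = 1.115.

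| Assumed SD (min) | SE (min) | Lag difference giving 90% coverage (min) | Lag difference giving 80% coverage (min) | Coverage with a 3-min lag difference |
|---|---|---|---|---|
| 30 | 8.7 | 5.6 | 9.7 | 93.6% |
| 45 | 13.0 | 8.5 | 14.5 | 94.4% |
| 60 | 17.3 | 11.3 | 19.3 | 94.7% |

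A 3-minute difference is negligible. Differences approaching half a scan interval are not.

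**Step 3: simulation check.** 40,000 trials, 24 per arm, order-clock SD 45 min, independent lag SD 15 min, true randomisation-to-completion difference 0:

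| lag_T − lag_C (min) | Mean difference, order clock (min) | Coverage, order clock |
|---|---|---|
| −15 | +15.0 | 0.80 |
| −10 | +10.0 | 0.88 |
| 0 | 0.0 | 0.95 |
| +10 | −9.9 | 0.88 |
| +15 | −15.0 | 0.80 |

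The randomisation clock gave a mean difference of about 0 and coverage of 0.95 in every row. With a true difference of 20 min, the order clock gave 34.9, 30.1, 20.0, 10.0 and 5.0 min down the same rows; the randomisation clock gave 20 throughout.

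**The case against.** The strongest reply is that harm is possible but not shown. No section says the arm will affect when the order is placed. The discretion over fluids and catheterisation concerns bladder filling, not ordering. Section 20/21.k's reasoning that these complaints may be life-threatening also argues against long waits. This stands as a limit on what can be claimed: the size and direction of the bias are unknown, and it may be zero. It does not supply the missing rule on order timing.

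A second reply is that order-to-image time is a sensible operational measure of preparation and imaging, whereas a randomisation clock also counts decision time before the order. That is a good reason to keep it as a secondary outcome. As the primary outcome it gives an unbiased randomised comparison only if order timing is alike in the arms.

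Third, total ED length of stay is recorded (17.a), and a large delay before the order might show there. It is a coarse check and is not named as an outcome, so it mitigates the problem without curing it.

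Fourth, a patient who is never ordered or scanned has no completion time under either clock. That is true; it does not favour the order clock, and an analysis plan can settle it.

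Finally, changing the clock may cost precision, and no equivalence margin is stated, so the chance of a false equivalence finding cannot be computed. Both points stand.

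**Conclusion.** The concern holds and should be fixed. As written, the primary clock can start after randomisation, at a time set by a clinician who can be inferred to know the arm. Any difference in mean order lag passes minute for minute, with reversed sign, into the primary result. That follows from the identity alone. How much it matters depends on lags and SDs that the protocol does not give: under assumed SDs of 30 to 60 min, coverage falls to 90% at lag differences of 5.6 to 11.3 min, in either direction. Confidence is medium, because differential ordering is a route the design leaves open and not something the protocol shows will happen.

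**What to change.** Define the primary outcome as time from randomisation to pelvic ultrasound image completion, in all randomised patients by assigned arm, and name randomisation time as a recorded item. Keep order-to-image time as a secondary outcome and report the randomisation-to-order interval by arm. State how patients who are never scanned will be handled.

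The administrative cost is protocol wording and one timestamp, with no extra procedures. The statistical cost is probably a wider CI, since the pre-order interval is now included. With an assumed order-clock SD of 45 min, lag SD L and correlation r between lag and order-to-image time, the new SD is √(45² + L² + 2 × r × 45 × L):

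| L (min) | r = −0.3 | r = 0 | r = +0.3 |
|---|---|---|---|
| 15 | 43.0 (−5%) | 47.4 (+5%) | 51.5 (+14%) |
| 30 | 46.0 (+2%) | 54.1 (+20%) | 61.1 (+36%) |

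Holding the CI width at L = 30 would need (54.1/45)² = 1.44 times the patients, about 35 per arm, if r = 0; or (61.1/45)² = 1.84 times, about 44 per arm, if r = +0.3. At L = 15 and r = 0 the factor is (47.4/45)² = 1.11, about 27 per arm.

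The alternative is to keep the order clock and randomise only once the order is placed. This also removes the bias route, but it gives up the pre-order enrolment described in Sections 16.d, 17.a and 21.c.

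### The primary outcome clock starts at the ultrasound order, which can follow randomisation, so an arm-dependent difference in order timing is left out of the comparison

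*Protocol*

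**What the plan says.** **Clock.** Item 14.b runs the primary outcome over "time from transabdominal pelvic ultrasound order placed to time of transabdominal pelvic ultrasound image completion". Item 14.a hypothesises equivalent time to completion under the new workflow.

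**Entry.** The order need not exist when a patient joins. The inclusion criterion in 16.d reads "Likely to have order placed for transabdominal pelvic ultrasound/ovarian ultrasound", and 17.a enrols patients for whom the clinician "anticipates ordering a transabdominal pelvic/ovarian torsion ultrasound". After eligibility and consent, "the patient will be randomized into the control or the treatment group" (17.a).

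**Treatment arm.** "This ultrasound will be obtained immediately upon enrollment and serially at 30-minute intervals" (17.a). If the bladder is not full, "the patient will receive additional hydration during the interval between repeated ultrasound examinations" (17.a). Item 16.e adds: "When the bladder is determined to be full, the transabdominal pelvic ultrasound will be performed". That sentence says when imaging is performed. No item says when it is ordered.

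**Control arm.** Current practice in 14.a "is to have a bladder catheter placed immediately when a transabdominal pelvic ultrasound is ordered". Item 17.a leaves both catheterisation and imaging time in this arm to the treating team.

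**Times recorded.** The medical-record fields in 17.a include order time, completion time, total emergency department stay and door-to-provider time. Randomisation time is not among them. Item 17.a also says that time to a successful ultrasound will be recorded, without giving a start point.

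**The concern.** The two workflows are anchored to different events. Treatment-arm filling is tied to enrolment, and control filling is normally tied to the order. The outcome uses only the order as its start. Because the order can come after the arm is known, the start of the clock is itself a post-randomisation event that the assigned workflow may influence.

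The protocol describes blinding only for the reviewers of stored bladder images. Treating clinicians decide on intravenous fluids in the treatment arm, so they can know the allocation. A clinician who sees that the bladder is still filling could reasonably hold the order until it is full; no intent to bias is needed. The wait would then fall before the clock starts.

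What is at stake is the main time claim. Waiting for the bladder to fill is the obvious time cost of the new workflow. An order-based clock could show equal or shorter times although treatment-arm patients waited longer from randomisation. If control orders were the later ones, it could instead make the new workflow look slower than it is.

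**Working it through.** The protocol gives no standard deviation, margin or power figure for this outcome, so there is no stated result to reproduce. The check is an identity plus an illustration.

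**Inputs.** 24 patients per arm (16.e); 24 + 24 = 48 agrees with the total in 16.a. Scan interval 30 minutes (17.a).

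**Step 1: split the time.** For each patient:

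(completion − randomisation) = (completion − order) + (order − randomisation)

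Call the last term the gap. Averaging within arms and subtracting control from treatment gives:

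D_random = D_order + (mean gap, treatment − mean gap, control)

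The primary outcome estimates D_order. The bracket is what it leaves out. It is zero if orders come equally soon after randomisation in both arms, positive if treatment-arm orders come later, and negative if control orders come later.

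**Step 2: effect of one late order.** Hold a patient's completion time fixed and move the order one scan interval later. That patient's order-to-completion time falls by 30 minutes, and the arm mean falls by 30 / 24 = 1.25 minutes.

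| Treatment-arm patients with an order 30 minutes later | Reduction in that arm's mean |
|---|---|
| 6 | 6 × 1.25 = 7.5 min |
| 12 | 12 × 1.25 = 15 min |
| 24 | 24 × 1.25 = 30 min |

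**Step 3: how a delay disappears.** Suppose treatment-arm patients truly wait 15 minutes longer from randomisation, and half of them are ordered 30 minutes later than they otherwise would be, with control gaps matching the rest. Then D_order = 15 − 15 = 0, and the primary outcome shows no difference. If instead half the control orders are 30 minutes later and true waits are equal, D_order = 0 − (−15) = +15 minutes, against treatment.

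**Step 4: would such a shift matter at this sample size?** This needs a standard deviation, which is assumed here at 30, 60 or 90 minutes. Take equal true randomisation-to-completion times and a mean gap 30 minutes longer in the treatment arm. With 24 per arm and a two-sided 5% test (normal approximation), the standard error is SD × √(2/24). The chance of a significant result favouring treatment is about 93%, 41% or 21% respectively.

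**The case against.** The strongest reply is that the protocol nowhere says treatment-arm orders come later. If orders are placed at or near enrolment in both arms, treatment-arm filling falls inside the clock and nothing is lost. This stands. A reader might take the 16.e wording to mean that the order waits for a full bladder, and so conclude that the outcome is biased towards treatment. The text does not support that: it speaks of performing the scan, not ordering it, and control timing is discretionary, so the shift could run the other way.

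A reader might also infer a range of 0 to 120 minutes for the effect, from the maximum of five scans in 17.e (4 × 30 = 120). Neither end is a true bound. The gap difference can be negative, and nothing forces an order by the fifth scan. As an illustration, 120 minutes would also be extreme: a patient's own sensation of fullness can end the wait (17.a), and a catheter may still be used if filling is unsuccessful (19.c.iii).

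Nor do the documents show that randomisation time goes uncollected. The 17.a list covers medical-record items only, and 23.a mentions paper data collection and an enrolment log. The protocol simply does not state that this time is captured.

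Finally, a randomisation-based time is no pure measure of filling. A late order for any reason lengthens it, so it also includes clinical decision delay. That is a reason to report the randomisation-to-order part separately, not a reason to leave the whole interval unmeasured. Total stay contains the wait but much else too, and is not among the outcomes named in 14.b.

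An analysis plan could add the extra analysis. It could not analyse a time that was never recorded, and the outcome definition itself is fixed in this document.

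**Conclusion.** The point holds as a risk of bias in the primary comparison. The clock starts at an event that can follow randomisation and that the known allocation can influence, and no provision ties the order to randomisation. The error in the primary contrast equals the between-arm difference in mean randomisation-to-order time. Its sign and size are not fixed by the protocol, and it may be zero. The 1.25 minutes per patient, or 15 minutes if half of one arm is affected, rest on 24 patients in the arm, a shift of one scan interval and unchanged completion times. They are illustrations, not expected values. The percentages rest further on assumed standard deviations. The change is worth making because it is cheap and because, without it, a finding of equivalent time could not be defended against arm-dependent ordering.

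**What to change.** Record the time of randomisation for every patient in both arms, on the study form or the enrolment log. Report randomisation-to-ultrasound-completion time and randomisation-to-order time by arm beside the order-based primary outcome. State in the protocol that equivalence in time will be concluded only if the randomisation-based result is consistent with it.

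Alternatively, require the order to be placed before randomisation. The start of the clock can then no longer depend on the arm, and all filling after allocation is counted. Consent could still be sought while the order is only anticipated, but randomisation would have to follow the order promptly, since usual practice places the catheter straight after it.

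The cost of the first option is one time stamp for 48 patients and a small added analysis. Its downside is a second time measure that includes clinical decision delay and may disagree with the primary outcome, in which case the difference must be explained.
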